The purpose of this pilot study is to examine the acceptability and proof of concept effectiveness of a wireless, transcranial direct current stimulation for people with cognitive impairments. Sample size (n=10) is convenient and designed to explore acceptability and feasibility. Participants who are enrolled will be provided a tDCS device to use for a period of four weeks. They will have two study visits, baseline (BL) and the 4th week visit (V1). During each visit participants will answer various questionnaires to assess patient-reported outcomes such as sleep quality, cognitive impairment, depression, anxiety, fatigue, and user acceptability.

Section E: Protocol Risks/Subjects

E1. Risk Category

Category 1: Research not involving greater than minimum risk.

E2. Subjects

Gender:

Both

Age:

Adult (18-64 yrs), Geriatric (65+ yrs)

Ethnicity:

All Ethnicities

Primary Language:

English, Spanish

Groups to be recruited will include:

Both patients and healthy, non-patient, normals

Which if any of the following vulnerable populations will be recruited as subjects?

Vulnerable populations require special protections. How will you obtain informed consent, protect subject confidentiality, and prevent undue coercion?

E3. Pregnant woman/fetus

Will pregnant women and/or fetuses (as described in 45 CFR 46 Subpart B) be enrolled in the research?

No

E4. Neonates

Will neonates of uncertain viability or nonviable neonates (as described in 45 CFR 46 Subpart B) be enrolled in the research?

No

E5. Children

Will children be enrolled in the research?

No

Section F: Design/Procedure

F1. Design

Select one category that most adequately describes your research:

c) Pilot

Discuss the research design including but not limited to such issues as: probability of group assignment, potential for subject to be randomized to placebo group, use of control subjects, etc.

We will prospectively recruit 10 subjects with cognitive issues such as poor working memory, brain fog, or impairments due to dementia, Alzheimer's, or concussions. This will be a single-arm study, providing all recruited subjects with the tDCS treatment. All subjects will be followed and monitored for up to 4-weeks.

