At the baseline visit (BL) patients will receive the tDCS device (LIFTiD Neurostimulation, RPW Technology, LLC, NY, USA) and research staff will provide instruction on how to use the device along with a user manual. Patients will be asked to use the stimulation device for at maximum 20 minutes per day, for a period of 4-weeks. Finally, at the BL visit patients will also be asked to answer a number of questionnaires to assess patient-reported outcomes and cognition. These include: instrumental activity of daily living scale (IADL), daily living independence (KATZ), depression (CES-D), fatigue (FACIT), cognitive assessment (MOCA), attention(Number Span forward) working memory (Number Span backward), processing speed and executive functioning (Trail Making Test Part A and Part B), and memory encoding, recall, and recognition (Hopkins Verbal Learning Test), pain and mobility, global health (PROMIS), sleep (PSQI), frailty (TSFI, FRIED FRAILTY), anxiety (BAI), multi-dimensional assessment of fatigue (MAF), community engagement (Life-Space), and user acceptability (TAM).

At the final visit (V1), patients will return to the clinic and return the neurostimulation device. To assess feasibility and acceptability (Aim 1), patients will answer a technology acceptance model (TAM) questionnaire. This questionnaire will assess their perceived ease of use, perceived benefit and technology anxiety. Furthermore, patients will answer the same questionnaires assessed at baseline in order to address Aim 2. Both aims are listed below: - Aim 1: To examine feasibility and acceptability of tDCS in patients with cognitive issues.

- Aim 2: To examine effectiveness of tDCS in patients with cognitive issues.

Device: LIFTiD neurostimulation uses transcranial direct current stimulation (tDCS) technology and was developed to help improve the brain's potential through electrical stimulation. Patients will be given the LIFTiD device headband, 1 mirror, 1 plastic spoon, 6 white sponges, 1 USB cable and 1 plastic bottle in a packet at the BL visit.

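### F2 repeats the cognitive performance tests at week 4 without specifying alternate versions, so in this single-arm study any practice gain would be part of the estimated tDCS effect

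*Combined protocol and SAP*

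**What the plan says.** All of this is in the combined protocol and SAP.

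- **Design (F1).** "This will be a single-arm study, providing all recruited subjects with the tDCS treatment". Section O1 answers No on placebo control. Section D sets two visits, baseline and week 4.
- **Baseline tests (F2).** Subjects will "answer a number of questionnaires to assess patient-reported outcomes and cognition". The list mixes self-report scales with performance tests. The latter are the MOCA, Number Span in both directions, both parts of Trail Making, and a word-list test described as covering "memory encoding, recall, and recognition (Hopkins Verbal Learning Test").
- **Week 4 (F2).** "patients will answer the same questionnaires assessed at baseline in order to address Aim 2".
- **Aim (F2).** "Aim 2: To examine effectiveness of tDCS in patients with cognitive issues".
- **Analysis (G2).** Mixed models or GEE, adjusted for covariates, are to test for an effect of the intervention on every outcome. G2 also describes a baseline comparison of two groups, AG and PG, which the design does not contain.

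No section mentions alternate or parallel versions, a practice session, a second baseline, reference data on retest change, or a caveat about practice.

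**The concern.** A performance test can be done better the second time because the person remembers items from the first sitting or knows what the task requires. A word list, the recall items of a screening test and a fixed trail layout are all open to this. A gain of this kind points the same way as the hoped-for benefit.

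With one treated arm, the only contrast available for Aim 2 is the change from baseline to V1, so whatever practice contributes is inside the estimate. It would fall on the direct measures of memory, attention and executive function, which are the outcomes closest to the purpose of the study. Sections D and G1 both present the trial as giving proof-of-concept information on effectiveness, and an improvement on these tests is what a reader would take as that evidence.

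The point concerns the performance tests. The self-report scales (PSQI, BAI, CES-D and others) have their own problems in an uncontrolled comparison, but not this one.

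**Working it through.** **No figure to reproduce.** G1 gives 10 subjects as a convenience number. The documents state no alpha, power, effect size, SD, retest correlation or retest gain.

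**Structure.** Write the expected change on a test as

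E(V1 − BL) = device effect + practice gain + other time effects.

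With one arm there is one mean change and no second equation, so the terms cannot be separated. A control arm tested on the same schedule would separate them. In simulation (200,000 runs, equal gain in both arms of 0.2, 0.5 or 0.8 SD of change), the two-sided type I error of a two-arm comparison of change stayed at 0.050, with 5 or 10 subjects per arm. The groups AG and PG in G2 cannot play this role, because F1 and O1 provide no second group.

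**Illustration of size.**

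- From the documents: n = 10.
- Assumed: all 10 complete; paired t-test on change; two-sided alpha 0.05; zero device effect; equal SDs at the two visits; retest correlation r of 0.5, 0.7 or 0.8; practice gain g of 0.2, 0.3 or 0.5 baseline SD.

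Formulas:

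- SD of change, in baseline SDs: s = √(2(1 − r)). This gives 1.000 at r = 0.5, 0.775 at 0.7 and 0.632 at 0.8.
- Standardised gain d = g/s; noncentrality λ = d√10.
- Chance of a significant result favouring tDCS = P(T > 2.262), where T is noncentral t with 9 df and noncentrality λ.

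Worked case, r = 0.7 and g = 0.3: d = 0.3/0.775 = 0.387; λ = 0.387 × 3.162 = 1.22; probability 0.194.

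| Practice gain (baseline SD) | r = 0.5 | r = 0.7 | r = 0.8 |
|---|---|---|---|
| 0 | 2.5% | 2.5% | 2.5% |
| 0.2 | 8.2% | 11.0% | 14.4% |
| 0.3 | 13.4% | 19.4% | 26.9% |
| 0.5 | 29.3% | 44.6% | 60.6% |

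**Sensitivity at r = 0.7.** A gain of 0.1 SD gives 5.6%. With 8 completers, gains of 0.2, 0.3 and 0.5 SD give 9%, 16% and 35%.

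These figures are per test. They use a paired t-test for simplicity; G2 plans covariate-adjusted mixed models or GEE.

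**The case against.** - **Silence is not a decision.** A reader might infer that the plan has chosen to give identical forms twice. The documents do not support that. The phrase about the same questionnaires covers the whole battery, self-report scales included, and can be read as naming instruments rather than forms. What can be said is that versions are not specified. This part of the objection stands.
- **The gain is not established.** A reader might also infer that the cognitive results are certain to be biased upward. No section gives a practice effect for any test, over four weeks or in this population. F1 admits people with dementia or Alzheimer's disease, in whom a gain may be small. This stands too: the claim is that any gain would be counted, not that one will occur.
- **The percentages are assumption-driven.** This is true, and they shrink with a lower retest correlation, a smaller gain or fewer completers. They also describe a simpler test than the one planned. A different model does not remove the confounding, since with one arm its time effect still contains practice.
- **It is a pilot.** Section D says the sample is meant to explore acceptability and feasibility, no cognitive test is named as primary, and F1's outcome list includes only MOCA among the performance tests. This lowers the stakes. It does not remove the point, because Aim 2 is effectiveness and G2 plans tests of it.
- **Parallel versions are not a cure.** They reduce learning of specific items but leave familiarity with the task, and expectancy and regression to the mean also remain. Their benefit cannot be computed from the documents. It would therefore be wrong to infer that change on a test with swapped versions becomes evidence of effectiveness. This stands, and the limit on interpretation must cover every performance test.

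**Conclusion.** The concern holds in this form: F2 repeats the performance tests at V1 for Aim 2 without specifying alternate versions, and the single-arm design and the analysis in G2 have no means of separating a practice gain from a tDCS effect. That conclusion rests on the text alone.

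The size is illustrative only. Under the assumed gains of 0.2 to 0.5 baseline SD and retest correlations of 0.5 to 0.8, a device with no effect would appear significantly beneficial on a given test in about 8% to 61% of such studies, against a nominal 2.5%.

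This should be changed, and the change is cheap. Versions have to be settled before baseline testing, because exposure to the items cannot be undone afterwards.

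**What to change.** **F2.** State that parallel versions will be used at BL and V1 wherever they are available in the subject's test language: a different Hopkins word list, a different MOCA version and different Number Span digit strings. Alternate the order of versions across the 10 subjects, five starting with each, so that differences in version difficulty tend to cancel.

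**G2.** State that pre-post change on all performance tests, with or without parallel versions, will be reported descriptively with confidence intervals, that it may include residual practice, and that it will not be attributed to tDCS as evidence of effectiveness. Reconcile the AG and PG wording with the single-arm design in F1.

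**Cost.** A short protocol edit and a version-allocation list, with no extra visit or arm. Scores will be slightly noisier because versions are not perfectly equal in difficulty. The balance of version order may be imperfect if subjects drop out. E2 lists English and Spanish as primary languages, so versions may have to be found in both.

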The patients will have two study visits where we will assess patient-reported outcomes through validated questionnaires. These include: instrumental activity of daily living scale (IADL), daily living independence (KATZ), depression (CES-D), fatigue (FACIT), cognitive assessment (MOCA), pain and mobility, global health (PROMIS), sleep (PSQI), frailty (TSFI, FRIED FRAILTY), anxiety (BAI), multi-dimensional assessment of fatigue (MAF), community engagement (Life-Space), and user acceptability (TAM).

Inclusion Criteria:

Adults (aged 18+) suffering from poor working memory, brain fog, or cognitive impairments (such as dementia, Alzheimer's, concussions, etc); ability to attend to the clinic for visits

Exclusion Criteria:

Severe cognitive decline that reduces their ability to interact with the tDCS device; Major visual or hearing weakness reduces the ability to interact with tDCS device; Major foot problems such as active lower extremity wounds, major foot deformity (e.g., Charcot Foot), previous major amputations, and claudication; Demand-type cardiac pacemaker, implanted defibrillator, implanted metal plate in the brain or head, or other implanted electronic devices; Epilepsy, seizures, brain lesions, migraine or severe heart disease; Sensitive skin or rash, broken skin, or open wounds; Pregnancy; and any conditions that may interfere with outcomes or increase the risk of the use tDCS based on the judgement of clinicians.

F2. Procedure

Please note that subjects will be consented before participating in any study-related activities. This study will not bring any direct costs to the subject.

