Preparation of device: 1. Patients must prepare a salt water solution in the plastic bottle provided using none iodized salt, tap water, and the provided measuring spoon. 2. Two sponges should be dampened with tap water and then saturated with the salt water solution made in step 1 on both sides. 3. Sponges should be placed in the electrodes in the LIFTiD headband. 4. LIFTiD headband should be placed on the forehead, centered and straight across. 5. Once fit, patient should

use the on/off button to begin stimulation. 6. Device automatically powers down after 20 minutes.

Stimulation frequency: maximum of 20 minutes daily. During the Stimulation the patient should perform an activity, such as read, answer emails, homework, etc.

After the completion of the study the patient should return the LIFTID device to the Research Coordinator.

All in-person visits will occur at Baylor College of Medicine McNair Campus. Research staff may call patients in between the two visits to assess compliance and answer questions. Patients will not be paid for in person visits or phone calls.

Section G: Sample Size/Data Analysis

G1. Sample Size

How many subjects (or specimens, or charts) will be used in this study?

Local: 10 Worldwide: 10

Please indicate why you chose the sample size proposed:

Convenient and selected based on available resources to demonstrate feasibility and the proof of concept effectiveness of tDCS therapy. We plan to recruit 10 eligible subjects.

G2. Data Analysis

Provide a description of your plan for data analysis. State the types of comparisons you plan (e.g. comparison of means, comparison of proportions, regressions, analysis of variance). Which is the PRIMARY comparison/analysis? How will the analyses proposed relate to the primary purposes of your study?

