Independent t-test, U-test, or Chi-square (depends on type of variables) to compare between groups (AG, and PG for key baseline descriptors including demographics and relevant clinical characteristics. Those descriptors which show statistical significant difference, baseline value of the outcomes measured in the model, and other variables that are deemed to be prognostic, will be considered as covariates for adjusting the results in the following assessments. Appropriate mixed models (linear for continuous or Generalized Estimating Equations (GEEs) for non-continuous or non-parametric variables) will be used to test the intervention effect for each of the outcomes. Results will be adjusted by covariates as described above.

Section H: Potential Risks/Discomforts

H1. Potential Risks/Discomforts

Describe and assess any potential risks/discomforts; (physical, psychological, social, legal, or other) and assess the likelihood and seriousness of such risks:

The devices and technologies are completely non-invasive, safe, non-toxic and non-ionizing. The potential risks to subject are minimal. However, like any battery powered systems, there is a minimum risk of sensor malfunctioning. In addition, the study devices are not waterproof, and although they use a low powered battery (similar to a cellphone battery), in order to avoid any risk of shock the monitor should not be submerged or saturated with fluids during operations or cleaning. It does not emit any radiation to the human body, and does not offer any significant risk to the subject.

Subjects may experience mild discomfort or irritation from the band or sponges on their forehead and mild headaches during adaptation period after initiating therapy. We will inform the subject to please notify the investigators if the band or sponges are uncomfortable.

All information we will collect about the subject will be stored in a secure location and coded in a way to maintain confidentiality. Only study personnel will have access to their records. Data collected during the study may be published and made publicly available. Data may also be shared with other research groups. However, data that could in any way identify them will not be made public or shared.

H2. Data and safety monitoring plan

Do the study activities impart greater than minimal risk to subjects?

No

H3. Coordination of information among sites for multi-site research

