Discuss the potential for psychological, social, and/or physical harm subsequent to participation in this research. Please discuss, considering the following areas: risks to privacy, confidentiality, insurability, employability, immigration status, paternity status, educational opportunities, or social stigma.

Will subjects be offered any type of genetic education or counseling, and if so, who will provide the education or counseling and under what conditions will it be provided? If there is the possibility that a family's pedigree will be presented or published, please describe how you will protect family member's confidentiality?

Section N: Sample Collection

None

Section O: Drug Studies

Does the research involve the use of ANY drug* or biologic? (*A drug is defined as any substance that is used to elicit a pharmacologic or physiologic response whether it is for treatment or diagnostic purposes)

No

Does the research involve the use of ANY gene transfer agent for human gene transfer research?

No

O1. Current Drugs

Is this study placebo-controlled?

No

Will the research involve a radioactive drug?

No

Section P: Device Studies

Does this research study involve the use of ANY device?

Yes

[Device 1: Transcranial Direct Current Stimulation \(tDCS\) Device](#)

Section Q: Consent Form(s)

Electrical Stimulation for Cognitive Issues

Section R: Advertisements

None

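### Aim 2 and Section G2 claim to test an effect of tDCS that a single-arm, two-visit design cannot identify; the study can only describe change from baseline

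*Combined protocol and SAP*

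**What the plan says.** **Design.** Section F1: "This will be a single-arm study, providing all recruited subjects with the tDCS treatment". Section D gives two visits, BL and V1 at week 4, and 10 subjects as a convenience sample. Section O, in its drug-study questions, also records "Is this study placebo-controlled? No". No run-in, repeated baseline, historical control or external benchmark is described.

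**Claim.** Section F2 lists "Aim 2: To examine effectiveness of tDCS in patients with cognitive issues". Section D is softer: "The purpose of this pilot study is to examine the acceptability and proof of concept effectiveness of a wireless, transcranial direct current stimulation". G1 uses the same proof-of-concept language. Aim 2 itself and G2 carry no such qualifier.

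**Analysis.** G2 opens with tests "to compare between groups (AG, and PG for key baseline descriptors including demographics and relevant clinical characteristics". Descriptors that differ significantly between those groups become covariates, together with the baseline value of the outcome and variables thought prognostic. Mixed models or GEE "will be used to test the intervention effect for each of the outcomes". Neither AG nor PG is defined anywhere.

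**Population and procedure.** Inclusion covers "Adults (aged 18+) suffering from poor working memory, brain fog, or cognitive impairments (such as dementia, Alzheimer's, concussions, etc"), with no requirement on duration or stability. F2 adds: "During the Stimulation the patient should perform an activity, such as read, answer emails, homework, etc". V1 repeats the baseline instruments to address Aim 2. The F2 baseline list includes MoCA, Number Span, Trail Making and the Hopkins Verbal Learning Test, as well as the self-report scales.

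**The concern.** Aim 2 and G2 promise a treatment effect, but the only contrast the data can supply is V1 minus BL in treated people. That difference contains any device effect plus at least five other things:

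- practice on performance tests taken twice, four weeks apart;
- expectancy on self-report scales, in people who know they are treated;
- regression to the mean, because subjects are selected for current complaints;
- the self-chosen activity done during each session;
- whatever natural course a mixed population with no duration limit happens to have, in either direction.

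No covariate adjustment separates these from the device. At stake is how Aim 2 can be interpreted: under the current wording, a significant pre-post change could be read as evidence that tDCS works, and a null change as evidence that it does not. Neither reading would be supported. In addition, the G2 plan cannot be run as written, because it compares groups that F1 does not create.

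**Working it through.** The plan gives no alpha, power, effect size or SD, and N = 10 is declared convenient, so there is no stated figure to reproduce. Three checks apply.

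**1. Can the effect be identified?** Take 10 subjects × 2 visits, with columns for intercept, time (0 at BL, 1 at V1) and tDCS.

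- Single arm: every subject is untreated at BL and treated by V1, so the tDCS column equals the time column. The matrix has rank 2 with 3 parameters. Only the sum (time effect + tDCS effect) is estimable, and adding subjects does not change the rank.
- Two arms, one untreated: rank 3 of 3, so the effect is estimable.
- G2 read literally, with intercept, group and time but only one group present: rank 2 of 3. The group term has no content.

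**2. How often would a pre-post test find benefit if the device did nothing?** Inputs: n = 10 from the protocol. Assumed, because the documents give none of these: two-sided alpha 0.05, normal changes, equal SD at both visits, non-device drift of 0.3 or 0.5 baseline SD in the favourable direction, and BL-V1 correlation r from 0.3 to 0.9.

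- SD of change, in baseline SDs = √(2(1 − r))
- Noncentrality = (drift / SD of change) × √10
- Critical t on 9 df = 2.262. The result is the upper-tail probability of the noncentral t beyond that value.

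Worked case, r = 0.7 and drift 0.3: SD of change = √0.6 = 0.775; 0.3 / 0.775 = 0.387; × 3.162 = 1.225; probability 19.4%.

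| r | SD of change | drift 0.3 SD | drift 0.5 SD |
|---|---|---|---|
| 0.3 | 1.183 | 10.7% | 22.3% |
| 0.5 | 1.000 | 13.4% | 29.3% |
| 0.7 | 0.775 | 19.4% | 44.6% |
| 0.8 | 0.632 | 26.9% | 60.6% |
| 0.9 | 0.447 | 47.4% | 88.1% |

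With no drift the favourable tail would hold 2.5%. The problem is bias, not low power, so more subjects make it worse. With drift of 0.3 SD of change, rejection in either direction is 13.6% at n = 10, 24.7% at n = 20, 54.8% at n = 50 and 84.4% at n = 100.

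**3. What can n = 10 deliver?** The 95% CI half-width for mean within-person change is 2.262 / √10 = 0.715 SD of the change score. If only 8 complete (assumed dropout), it is 0.836 SD. This interval describes change from baseline, not a tDCS effect.

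**The case against.** The strongest reply is that this is a declared pilot. F1 selects that category, Section D says that the sample was designed to explore acceptability and feasibility, and a single arm is an ordinary choice for that. This stands. The design serves Aim 1, and a reader who infers that the study itself is unsound goes further than the documents allow. The fault lies in the wording of Aim 2 and G2, which lack the pilot qualifier. That a significant result would in fact be published as effectiveness is a prediction, not something that the protocol says.

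A reader might also infer that the eligible conditions recover on their own, or that the dementia cases will decline within four weeks. The documents state neither. They only admit these conditions without a duration limit, and they let clinicians exclude anything likely to interfere with outcomes. The point does not need either premise, since practice, expectancy or regression to the mean would each be enough.

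It could be said that a comparator exists, because G2 names AG and PG and Section E2 lists healthy subjects as well as patients. Neither supplies one. AG and PG are undefined, F1 treats everyone, and the inclusion criteria give healthy subjects no role. These are contradictions to reconcile. G2's allowance for prognostic covariates does not help either, because adjustment cannot separate two identical columns.

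Two limits on size also stand. Any single false-positive figure depends on an assumed drift and correlation, so only the range is defensible. The concurrent activity could total at most 28 × 20 = 560 minutes (9.3 hours), but 20 minutes is a daily maximum and reading or email may be what participants do anyway. It cannot be separated from the device, but it is not shown to be added exposure.

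**Conclusion.** The concern holds for the claim, not for the choice of a single-arm pilot. With one treated arm, two visits and no benchmark, the effect that Aim 2 and G2 set out to examine and test is not identifiable at any sample size. That conclusion follows from F1 and Section D alone and needs no assumed numbers.

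The size of the resulting error is illustrative: about 11–47% apparent benefit per outcome at 0.3 baseline SD of non-device drift and about 22–88% at 0.5 SD, with zero device effect. It rests on assumed drift, BL-V1 correlations of 0.3 to 0.9, a 5% two-sided test and normal changes. Aim 1 is unaffected. Aim 2 as written cannot be answered, and should be reworded before results are analysed.

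**What to change.** 1. Restate Aim 2, and align Section D and G1 with it, as estimating BL-to-V1 change in cognition and patient-reported outcomes during four weeks of open-label tDCS used with a concurrent activity.
2. In G2, remove the AG/PG comparison and the covariate rule that depends on it. Changing the intervention-effect phrase alone would leave a two-group plan that cannot be run.
3. In its place, specify mean within-person change with a 95% CI for each outcome, and note the expected precision (half-width about 0.72 SD of change at n = 10).
4. State that no effectiveness claim will be made from this study, and name practice, expectancy, regression to the mean, concurrent activity and natural course as possible explanations of any change.
5. Optionally, list individual changes by recorded cause of impairment, descriptively only. Ten subjects are too few for subgroup summaries.

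The cost is text in Sections D, F2, G1 and G2. No arm, visit, subject or treatment procedure changes. The downside is a more modest stated claim. If an effectiveness claim is wanted, the alternative is a concurrent control, which would be a different study.

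### G2 tests two undefined groups in a single-arm study and states neither the baseline-to-week-4 contrast nor a primary analysis

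*Combined protocol and SAP*

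**What the plan says.** **Design.** Section F1 states: "This will be a single-arm study, providing all recruited subjects with the tDCS treatment". It also says "We will prospectively recruit 10 subjects with cognitive issues", and its inclusion criteria admit only adults with such problems. There are two visits, BL and V1 at week 4.

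**Aims.** Section D says "The purpose of this pilot study is to examine the acceptability and proof of concept effectiveness". Section F2 separates this into Aim 1 (feasibility and acceptability) and Aim 2 (effectiveness), and says that at V1 "patients will answer the same questionnaires assessed at baseline in order to address Aim 2".

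**Analysis.** The form's G2 prompt asks "Which is the PRIMARY comparison/analysis". The answer has three parts:

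- Baseline comparison: "Independent t-test, U-test, or Chi-square (depends on type of variables) to compare between groups (AG, and PG for key baseline descriptors".
- Covariates, from three sources: "Those descriptors which show statistical significant difference, baseline value of the outcomes measured in the model", and other variables judged prognostic.
- Models: linear mixed models, or GEE where the outcome is not continuous, which "will be used to test the intervention effect for each of the outcomes".

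G2 mentions no visit or time term, no change from BL to V1, and no primary outcome or analysis.

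**The concern.** G2 is the only analysis plan in the document, and its first step presupposes two groups that the design does not contain. The covariate rule built on that step fails with it. The modelling step survives only once someone decides what effect the model estimates and which outcome leads. Neither choice is fixed in advance, so either could be made after the data are seen.

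The term used for the result matters too. With one treated group, the estimable quantity is a change over 4 weeks. Calling it an intervention effect attributes the whole change to the device.

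**Working it through.** The plan has no calculated figure to reproduce: G1 gives 10 subjects as a convenience number, with no error rate, power, SD or dropout. The check is mainly a comparison of texts.

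**1. Which G2 steps can be run on one undivided group of 10?**

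- Independent-samples tests of AG against PG: no, there is no second group.
- Covariates chosen by significant AG/PG difference: no, they depend on the first step.
- Covariates from the outcome's baseline value or prognostic judgement: yes, neither needs groups.
- Mixed model or GEE for a between-group effect: no. In a single arm the group indicator equals the intercept, so a design matrix with intercept, group and baseline has rank 2 of 3.
- Mixed model or GEE for a visit effect: yes. Intercept and visit have rank 2 of 2.

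The estimable effect is thus V1 minus BL. F2 implies it for Aim 2, but G2 does not state it.

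**2. How many outcomes compete for the leading place?** TAM is left out because it serves Aim 1.

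- F1 list: IADL, KATZ, CES-D, FACIT, MOCA, pain and mobility, PROMIS, PSQI, TSFI, Fried, BAI, MAF, Life-Space = 13.
- F2 list: these 13 plus Number Span forward, Number Span backward, Trail Making A, Trail Making B and Hopkins = 13 + 5 = 18.

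Both counts move by a few with how PROMIS, Hopkins, and pain and mobility are counted. As an illustration, assume each outcome is tested at a two-sided 5% level and nothing truly changes. The expected number of significant results is 13 × 0.05 = 0.65 or 18 × 0.05 = 0.90, whatever the correlation between measures.

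**3. Precision of the estimable contrast (context only).** The 95% CI half-width, in SDs of the change, is t(0.975, n−1)/√n:

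- n = 10: 2.262/3.162 = 0.72
- n = 9: 2.306/3 = 0.77
- n = 8: 2.365/2.828 = 0.84

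The values below 10 completers are assumptions. These widths follow from the sample size and are the same before and after the correction.

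**4. Should the outcome's own baseline stay as a covariate?** In a BL-to-V1 model the baseline value is already one of the two responses. Simulated data with a normal outcome and 10 complete pairs (300 sets per assumed correlation) gave the same time coefficient with or without it. The mixed-model standard error, however, averaged 0.943 of the paired one at a BL–V1 correlation of 0.5 and 0.970 at 0.8, so it was about 3% to 6% too small. With a binary outcome and a logit GEE (assumed subject SD 1.5 and shift 0.7 on the logit scale), adding baseline changed the time coefficient in about 70% of usable data sets, by a median of 0.18 log-odds. The covariate gains nothing here and should be left out.

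**The case against.** The strongest reply is that this is a declared pilot with a convenience sample. A sensible analyst would drop the group tests and fit a visit effect, since F2 makes the repeated measurement plain. That is fair for the modelling sentence, and the planned mixed model or GEE need not be replaced by paired tests. But pilot status excuses the sample size, not a plan whose first step does not fit its design, and the contrast belongs in G2.

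It can also be said that the primary purpose is visible: Section D ties the sample size to acceptability and feasibility, and Aim 1 comes first. Against this, Section D names proof-of-concept effectiveness in the same sentence as acceptability, and G1 repeats it in justifying the sample size. The accurate statement is that a primary analysis is not stated, not that no reader could guess one.

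On interpretation, practice effects bear mainly on the performance tests (MOCA, number spans, Trail Making, Hopkins), since most of the other measures are self-reported. The inclusion criteria set no score threshold, so regression to the mean is possible but not shown.

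Three stronger readings are tempting, and the documents do not support them:

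- **PG means a placebo group.** G2 does not expand the letters. The form's negative answer on placebo control sits in the drug section of a device study and settles nothing about them.
- **AG and PG are the patients and healthy subjects of Section E2.** Nothing links that entry to G2, and F1 and its inclusion criteria admit only people with cognitive problems.
- **None of G2 can be carried out.** Two covariate sources and the model sentence remain usable.

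**Conclusion.** The point holds and should be corrected before any data are analysed. Two steps of G2, the between-group baseline tests and the significance-based covariate rule, cannot be run under the design in F1. What remains can be run, but the Aim 2 contrast and the primary analysis are unstated, with about 13 or 18 measures open to selection. The defect is a contradiction and two omissions in the text. The half-width of 0.72 SD describes what 10 subjects can deliver and does not measure the defect.

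This rests on the text available, from which front matter had been removed. A definition of AG and PG there would still have to be reconciled with the single arm in F1. The 5% level and the correlations used above are assumptions.

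**What to change.** Rewrite the G2 paragraph as follows.

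1. Delete the AG/PG tests and the significance-based covariate rule, and describe baseline characteristics for the one group. If AG and PG are real subject-level groups, define them and reconcile them with F1.
2. State the Aim 2 analysis as within-subject change, V1 minus BL, with a 95% CI. Take it from the planned mixed model or GEE with a visit term and without the outcome's own baseline as a covariate, or from an equivalent paired analysis.
3. Name one primary analysis in advance, chosen by the investigators, and label the other outcomes exploratory. Settle which of the F1 and F2 measure lists applies.
4. Report Aim 2 as change from baseline, not as an intervention effect. Note that without a control, practice effects (mainly on the performance tests) and regression to the mean cannot be excluded.

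Two secondary points can be dealt with in the same edit: add a short feasibility summary for Aim 1, such as the number of the 10 who complete V1, and reconcile the healthy-subject entry in E2 with the inclusion criteria.

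The cost is one paragraph of wording, plus a definition in F1 if the groups are real. No visits, measures or subjects are added. The downside is a weaker stated claim for Aim 2.
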